7.9 Efficacy Analysis

Response will be assessed according to mRECIST 1.1 for all patients. Response will also be assessed according to iRECIST for patients in Phase 2 expansion cohort.

Best Overall Response (BOR)

Best overall response is defined as the best response (per investigator assessment as defined by mRECIST 1.1 or iRECIST Criteria) recorded after the first dose of the study drug until a subsequent anti-cancer therapy. Response assessments after treatment discontinuation but before the initiation of a subsequent anti-cancer therapy should be included in the analysis of BOR. This will be ordered from best to worst: Complete Response (CR or iCR), Partial Response (PR or iPR), Stable Disease (SD or iSD), Progressive Disease (PD, iUPD or iCPD), Not Evaluable (NE or iNE).

Waterfall plots for best percentage change in the size of target lesions as per mRECIST 1.1 criteria will also be presented. The plot will have the following information:

1. Response,
2. Dose,
3. Cohort
4. Phase (escalation, safety lead-in or expansion).

Best overall response will be summarized and listed for all patients in the response evaluable analysis set. Overall response will be listed for all patients in the response evaluable set for each visit along with percentage change in the size of target lesions per mRECIST 1.1 criteria. If target lesion is believed to be present but too small to measure, a value of 5 mm is assigned per mRECIST 1.1.

Overall Response Rate (ORR)

The ORR is defined as the proportion of patients who have achieved the best response of CR or PR during the study per investigator assessment as defined by mRECIST 1.1 or iRECIST Criteria. The ORR will be summarized by frequencies and percentages for patients in the response evaluable analysis set. A binomial exact confidence interval will also be provided when possible.

Disease Control Rate (DCR)

The DCR is defined as the proportion of patients who have achieved the best response of CR, PR or SD during the study per investigator assessment as defined by mRECIST 1.1 or iRECIST Criteria. The DCR will be summarized by frequencies and percentages for patients in the response evaluable analysis set. A binomial exact confidence interval will also be provided when possible.

Duration of Response (DOR)

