The DOR will be tabulated for those patients with a CR or PR during the study per investigator assessment as defined by mRECIST 1.1 or iRECIST Criteria in the response evaluable analysis set with a reasonable number of responses. The DOR is defined as the number of days from the first documentation of a response until progressive disease or death, whichever occurs first. If a patient misses two consecutive disease assessments, then follow-up for the primary endpoint will be censored at the time of last non-progressive scan prior to the missed interval.

The censoring rules and censoring date in the analysis of DOR will be the same as for PFS and TTP.

$$\text{DOR (months)} = (\text{date of progression or death or censor} - \text{date of confirmed response} + 1) / 30.4375.$$

The Kaplan-Meier method will be used to estimate the distribution of DOR. The 25th, 50th (median), and 75th percentiles, and the corresponding 2-sided 95% confidence intervals (CIs) based on Brookmeyer and Crowley method (Brookmeyer and Crowley 1982), will be presented. The number of patients with events and the number of patients censored will be summarized. DOR for all patients with a response will be listed.

Progression Free Survival (PFS)

PFS is defined as the time from the date of first dose to the date of PD (or iCPD) (per investigator assessment as defined by mRECIST 1.1 or iRECIST Criteria) or the date of death due to any cause, whichever occurs first. Patients without documentation of PD (or iCPD) or death will be censored at the date of the last response assessment that is SD (iSD) or better, and prior to or on the date of initiation of alternative anti-cancer therapy if patients start new treatments. Patients with no post baseline response assessment will be censored on day 1.

$$\text{PFS (months)} = (\text{earliest date of progression or death or censor} - \text{date of first dose} + 1) / 30.4375.$$

The analysis of PFS will be based on the safety analysis set with a reasonable number of patients. The Kaplan-Meier method will be used to estimate the distribution of PFS. Kaplan-Meier survival curves, the 25th, 50th (median), and 75th percentiles, along with associated 2-sided 95% confidence intervals (CIs) based on Brookmeyer and Crowley method, and Kaplan-Meier PFS

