probability estimates with 95% CIs at 3 and 6 months (or later time points if data permits) will be presented. The number of patients with events along with the type of events (death or progressive disease) and the number of patients censored will be summarized.

PFS for all patients in the safety analysis set will be listed.

Overall Survival (OS)

Overall survival in months is defined as the time from the date of first dose to the date of death of any cause [OS (months) = (date of death or censor – date of first dose + 1)/30.4375]. Patients without documentation of death at the time of analysis will be censored at the date last known to be alive.

The analysis of OS will be based on the safety analysis set with a reasonable number of patients. The Kaplan-Meier method will be used to analyze the distribution of OS. Kaplan-Meier survival curves, the 25th, 50th (median), and 75th percentiles, along with associated 2-sided 95% confidence intervals (CIs) based on Brookmeyer and Crowley method, and Kaplan-Meier estimates with 95% CIs at 6 and 12 months (or later time points if data permits) will be presented. The number of patients with events and the number of patients censored will be summarized.

OS for all patients in the safety analysis set will be listed.

Time to Progression (TTP)

Time to progression is defined as the time from first dose to the date of first documentation of objective progression. Patients without documentation of PD (iCPD) will be censored at the date of the last response assessment that is SD or better prior to the date of initiation of alternative anti-cancer therapy. Patients with no post baseline response assessment will be censored on day 1.

$TTP \text{ (months)} = (\text{date of progression or censor} - \text{date of first dose} + 1) / 30.4375$.

The Kaplan-Meier method will be used to estimate the distribution of TTP with a reasonable number of patients in the response evaluable set. Kaplan-Meier curves, the 25th, 50th (median), and 75th percentiles, along with associated 2-sided 95% confidence intervals (CIs) based on Brookmeyer and Crowley, and Kaplan-Meier estimates with 95% CIs at 3 and 6 months (or later time points if data permits) will be presented. The number of patients with events and the number of patients censored will be summarized.

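### iRECIST PFS: SAP 7.9 can censor a patient before an unconfirmed progression (iUPD), and it does not say how an iCPD event is dated

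*SAP*

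**What the plan says.** SAP 5.2 lists PFS, TTP and DOR by iRECIST as secondary endpoints for the phase 2 expansion. Protocol 13.4 plans no formal tests, and each cohort has up to 25 patients.

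SAP 7.9 contains these rules:

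- **PFS.** The event is PD (or iCPD) or death. Otherwise, "Patients without documentation of PD (or iCPD) or death will be censored at the date of the last response assessment", with the further condition that this assessment is SD (iSD) or better. Results include "probability estimates with 95% CIs at 3 and 6 months".
- **TTP.** The endpoint is "the time from first dose to the date of first documentation of objective progression", but the censoring sentence reads "Patients without documentation of PD (iCPD) will be censored at the date of the last response assessment that is SD or better".
- **DOR.** It is "the number of days from the first documentation of a response until progressive disease or death, whichever occurs first". Also, "The censoring rules and censoring date in the analysis of DOR will be the same as for PFS and TTP".
- **Best overall response.** One class holds all three progression categories, "Progressive Disease (PD, iUPD or iCPD", and it ranks below iSD.
- **Missed assessments.** "If a patient misses two consecutive disease assessments, then follow-up for the primary endpoint will be censored" at the last non-progressive scan. The sentence sits in the DOR paragraph.

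Protocol 9.3.14.1 lets patients continue past a first RECIST progression only if they are clinically stable and benefiting. It also lets the investigator stop a rapidly deteriorating patient before the next scan and report this as progression. Protocol 6.3.1, 9.7 and footnote t of the phase 2 Schedule of Events give PFS follow-up to patients who stop for reasons other than PD. For the iRECIST measures, protocol Table 6.a only refers back to the definitions above it.

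**The concern.** An iUPD is neither an event nor an allowed censoring date for iRECIST PFS. If no confirming scan follows and no death is counted, the SAP moves the patient back to the last iSD or better, and the progression disappears from the curve. The patients most exposed are those not stable enough to continue to a confirming scan, so their censoring is unlikely to be independent of prognosis. The estimate is then too high.

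A second gap concerns patients who are confirmed. Two programmers could follow SAP 7.9 and date the same iCPD one scan interval apart. At stake are the reported 3- and 6-month estimates and the median of a named secondary endpoint.

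**Working it through.** The plan states no target or event count for iRECIST PFS, so there is no figure to reproduce. The check is a trace of the text, then an illustration.

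**One patient.** Take iSD at day 42, iUPD at day 84, then a stop with no further scan or counted death. By the SAP formula, censoring falls at (42 + 1)/30.4375 = 1.41 months. An event at the iUPD would fall at (84 + 1)/30.4375 = 2.79 months.

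**No date at all.** If the first post-baseline scan is the iUPD, there is no assessment of iSD or better. The day-1 rule covers only patients with no post-baseline assessment, so the censoring date is undefined.

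**Illustration.** From the documents: scans at weeks 6, 12, 18, then every 9 weeks (protocol 9.3.14), and 3- and 6-month landmarks (weeks 13.04 and 26.09). Assumed: exponential time to progression with a 13-week median, no pseudoprogression, and 20% or 40% of patients unconfirmed. Kaplan–Meier estimates come from 400,000 simulated patients per scenario; an unconfirmed patient with no earlier scan is censored on day 1, a convention of the simulation.

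Reference, with every iUPD an event on its own date:

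- 3 months: 2^(−12/13) = 0.527
- 6 months: 2^(−18/13) = 0.383
- iUPD at the first scan: 1 − 2^(−6/13) = 27% of patients

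6-month PFS with iCPD dated at the iUPD:

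| Unconfirmed patients | 20% unconfirmed | 40% unconfirmed |
|---|---|---|
| All reported as progression before the next scan, and counted | 38.5% | 39% |
| Half so reported, half censored | 42% | 45% |
| None reported; deaths counted, 8-week median survival after progression | 42% | 45% |
| None reported; no later death counted | 45% | 54% |
| None reported; deaths counted, 40-week median | 47% | 56% |

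The last row moves by about a point either way with where the death clock starts. Counting deaths need not repair the estimate: a late death keeps the patient event-free beyond the progression. With none reported and 20% unconfirmed, other medians behave alike: 25% becomes 31–35% (9 weeks) and 62% becomes 68% (26 weeks).

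**Dating alone, 0% unconfirmed.** If iCPD is dated at the next scheduled scan and deaths are ignored, 3-month PFS is 2^(−6/13) = 0.726, a rise of 0.726 − 0.527 = 20 points. At 6 months it is 2^(−12/13) = 0.527, a rise of 0.527 − 0.383 = 14 points. That 6-month rise exists because a week-18 iUPD is confirmed at week 27, after the landmark. If confirmation comes 6 weeks after the iUPD (week 24), the 6-month rise is zero and the 3-month rise stays about 20 points. If iCPD is dated at the iUPD, both are zero.

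**Scale.** The standard error of 38% with 25 patients is √(0.383 × 0.617/25) = 9.7 points.

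**The case against.** The strongest reply is that the patients who would drive the bias may already be events. Protocol 9.3.14.1 allows deterioration before the next scan to be reported as progression, and SAP PFS rests on investigator assessment. If all unconfirmed patients are captured this way, almost nothing is left at 6 months (38.5% against 38.3%). Early deaths also shrink the effect. Both stand as limits on size, but the SAP does not map such a report to an iRECIST event, so the rule is not secured.

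Some patients who stop at an iUPD may still be scanned. Protocol 8.6.4.1 makes only confirmed PD a mandatory stop, and the follow-up sections do not say whether an unconfirmed PD counts as PD. A reader might infer that every patient who stops at an iUPD is censored early; the text supports only that some can be.

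A reader might also infer that the dating gap inflates the curve. Most of the wording leans the other way: the PFS formula takes the earliest date of progression, TTP uses first documentation, and Table 6.a points back to first-documentation definitions. Only the phrase giving the date of PD (or iCPD) can be read as the confirming scan.

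The iRECIST guideline is adopted by citation and may settle both matters, but it was not available to this review. Finally, requiring confirmation is a legitimate choice, the endpoint is descriptive, and by-patient listings would allow alternatives to be derived. That limits the consequence; it does not give the analysis a stated rule.

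**Conclusion.** The point holds for iRECIST PFS. As written, SAP 7.9 can censor a patient before an unconfirmed progression and leaves the censoring date undefined when that progression is at the first scan. The bias is likely upward. Its size depends on the unconfirmed rate, on later deaths, and on whether reported deterioration counts; the documents fix none of these. In the illustration, the excess at 6 months with iCPD dated at the iUPD runs from near zero to 7–9 points at 20% unconfirmed, and to 16–18 points at 40%. These upper values are not expected values.

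The iCPD date is a separate ambiguity. It adds about 20 points at 3 months and 0 to 14 at 6 months, and only if the confirming scan is used.

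iRECIST TTP and DOR are ambiguous rather than clearly biased, because their event wording could take in an iUPD while their censoring wording follows iCPD. RECIST v1.1 PFS and TTP, the primary ORR and OS are not affected. Neither document plans a comparison of iRECIST with RECIST PFS, so a reader should not infer that such a comparison is planned or biased; the risk is that an unexplained gap is read as benefit beyond progression. This should be fixed before the curves are seen, but it does not threaten the primary analysis.

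**What to change.** In SAP 7.9:

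1. For iRECIST PFS, TTP and DOR, count as an event, on the iUPD date, any iUPD that is later confirmed or is not followed by an assessment of iSD or better. This also settles an iUPD at the first scan.
2. Align the TTP and DOR event sentences with this rule and its dating.
3. State whether progression reported for deterioration under protocol 9.3.14.1 is an iRECIST event.
4. Report the iCPD-only version, with its dating stated, as a sensitivity analysis.

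The cost is SAP wording and one sensitivity table, with no new data. The iRECIST estimates would be slightly less favourable. An unconfirmed iUPD that was really pseudoprogression would count as an event; protocol 9.3.14.1 calls response after progression rare, and the sensitivity analysis shows the other reading.

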6.3 Duration of Study

6.3.1 Duration of an Individual Patient's Study Participation

Patients may receive modakafusp alfa as a SA for up to 1 year or in combination with pembrolizumab for up to 2 years. Patients with demonstrated clinical benefit can continue treatment beyond those points if approved by the sponsor. These patients can continue receiving treatment in this study or in any of the poststudy access modalities described in the protocol (Section 6.3.5). Patients may discontinue treatment when they meet any of the discontinuation criteria stated in the protocol (Section 9.6).

All patients will have an EOT visit 30 days (+10 days) after receiving the last dose of study drug or before the start of subsequent systemic anticancer therapy, whichever occurs first, to permit detection of any delayed TEAEs and to resolve any ongoing events. Patients with unresolved TEAEs will continue the periodic safety follow-up until complete resolution or stabilization (established as sequelae) occurs.

Patients who discontinue study treatment for reasons other than progressive disease (PD) will continue PFS follow-up every 12 ± 1 weeks from the EOT visit until the occurrence of PD, lost to follow-up, consent withdrawal, death, start of subsequent systemic anticancer therapy, or study termination, whichever occurs first. After disease progression or starting another systemic anticancer therapy, all patients will be followed every 12 ± 1 weeks for OS until death or study termination.

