9.7 Posttreatment Follow-up Assessments (PFS and OS)

Patients who stop treatment for any reason other than PD will continue to have PFS follow-up visits. The PFS follow-up should occur every 12 ± 1 weeks from the EOT until the occurrence of progression, death, the start of subsequent systemic antineoplastic therapy, study termination, or until 6 months after the discontinuation of study treatment, whichever occurs first.

After disease progression or starting another systemic anticancer therapy, all patients will be followed every 12 ± 1 weeks for OS until death or study termination. Survivor information and death details may be collected by methods that include, but are not limited to, telephone, e-mail, mail, or retrieval from online or other databases (eg, Social Security indexes). In addition, the start of another anticancer therapy for the disease under study will be collected.

See [Appendix A](#) for appropriate assessments during follow-up.

NOTE: Treatment-related SAEs must be reported to the Global Pharmacovigilance department or designee. This includes deaths that the investigator considers related to study drug that occur during the posttreatment follow-up. Refer to Section [10.0](#) for details regarding definitions, documentation, and reporting of SAEs.

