13.4 Efficacy Analysis

Efficacy endpoints include ORR, DCR, DOR, PFS, and OS. No formal statistical tests will be performed for these efficacy endpoints.

ORR is defined as the proportion of patients who achieve CR or PR (determined by the investigator) during the study in response-evaluable population.

DCR is defined as the proportion of patients who achieve CR, PR, or SD (determined by the investigator) during the study in response-evaluable population.

DOR is the time from the date of first documentation of a PR or better to the date of first documentation of PD for responders (PR or better). Responders without documentation of PD will be censored at the date of last response assessment that is SD or better.

TTP is the time from the date of the first dose of study drug to the date of the first documentation of PD according to RECIST v1.1.

PFS is defined as the time from the date of the first dose of study drug to the date of first documentation of PD according to RECIST v1.1 or death due to any cause, whichever occurs first. Patients without documentation of PD or death will be censored at the date of the last response assessment that is SD or better.

OS is defined as the time from the date of first dose of study drug to the date of death due to any cause. Patients without documentation of death at the time of analysis will be censored at the date last known to be alive.

ORR and DCR will be summarized using descriptive statistics with 95% CIs. PFS and OS will be analyzed descriptively using the Kaplan-Meier method for the safety analysis set. DOR will also be analyzed using the Kaplan-Meier method for the response-evaluable analysis set.

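### PFS censoring at new anti-cancer therapy depends on whether the patient later dies, and the DOR rule for the same patients contradicts itself

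*SAP*

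**What the plan says.** **Follow-up.** Protocol 6.3.1 keeps patients who stop treatment without progression in PFS follow-up "until the occurrence of PD, lost to follow-up, consent withdrawal, death, start of subsequent systemic anticancer therapy, or study termination". Protocol 9.7 has the same stop at new therapy, and the schedule-of-events footnotes repeat it. Survival follow-up goes on: "After disease progression or starting another systemic anticancer therapy, all patients will be followed every 12 ± 1 weeks for OS until death" or study termination.

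**PFS.** The SAP 7.9 event is progression "or the date of death due to any cause, whichever occurs first". The censoring sentence begins "Patients without documentation of PD (or iCPD) or death will be censored at the date of the last response assessment that is SD (iSD" and adds the condition "and prior to or on the date of initiation of alternative anti-cancer therapy if patients start new treatments". Protocol 13.4 has only "Patients without documentation of PD or death will be censored at the date of the last response assessment that is SD or better", with no mention of new therapy.

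**TTP and best overall response.** SAP 7.9 censors TTP for everyone without progression, including those who die, at the last assessment of stable disease or better before new therapy. Best overall response counts only assessments before subsequent therapy.

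**DOR.** The SAP event is progression or death, and its censoring is said to match both PFS and TTP. Protocol 13.4 counts progression only.

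**Missed assessments.** In its DOR paragraph, SAP 7.9 censors a patient who misses two consecutive assessments at the last non-progressive scan. It describes this as applying to follow-up for the primary endpoint. The SAP's summary of changes says the rule covers DOR, PFS and TTP.

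**The concern.** Kaplan-Meier estimation requires that whether and when a patient is censored does not depend on what happens to that patient afterwards. Here the limit at new therapy applies only to patients with no recorded death. Two patients with the same scans and the same switch date get different times at risk, depending on whether one of them later dies.

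The patient who dies is counted as progression-free through an interval on another treatment in which nobody was looking for progression. The patient who lives is taken out of the risk set at the last scan. The resulting curve mixes time to progression on modakafusp alfa plus pembrolizumab with survival on the next therapy. The cohorts are single-arm, so there is no comparator in which the same distortion would appear.

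**Working it through.** No figure in either document depends on this rule, so there is nothing to reproduce. The check is a reading of the rules, followed by an illustration under assumed rates.

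**1. Two patients under the literal wording.** Assumed dates: last stable-disease scan on study day 84, switch on day 98 without progression. SAP 7.9 converts days to months by dividing by 30.4375.
- Dies on day 420: documented death, so the censoring sentence does not apply. PFS event at 420 / 30.4375 = 13.8 months.
- Alive at cut-off: censored at the last scan on or before the switch, 84 / 30.4375 = 2.76 months.

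**2. The same patients if post-switch scans count as missed.** A death before the second missed scan remains an event. A later death, like that of the patient above, is censored at day 84, as is a survivor. The outcome still depends on when the patient dies. The SAP does not say which reading applies.

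**3. Illustration at cohort level.** Assumptions, none from the documents: exponential time to progression with median 4 months; exponential switching set so that 10%, 20% or 30% switch before progression; exponential survival after the switch with median 12 months; uniform follow-up of 12 to 36 months. The switch hazard for a proportion p is (ln 2 / 4) × p / (1 − p); at p = 0.20 this is 0.1733 × 0.25 = 0.0433 per month. The true 6-month progression-free proportion is 2^(−6/4) = 35.4%. Each scenario simulates 400,000 patients. Missed scans are counted on the grid in Protocol 9.3.14 (every 6 weeks through Cycle 6, then every 9).

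| Switch before progression | Literal SAP | Missed-scan rule applied | Consistent censoring |
|---|---|---|---|
| 10% | 36.1% | 35.0% | 35.3% |
| 20% | 37.3% | 34.5% | 35.3% |
| 30% | 38.6% | 33.9% | 35.4% |

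Entries are 6-month PFS. At 20% switching the literal rule is 37.3 − 35.3 = 2.0 points too high and the missed-scan rule 35.3 − 34.5 = 0.8 points too low. Under the missed-scan rule about 21 to 22% of post-switch deaths remain events. This version censors at the switch date, whereas the SAP censors at the preceding scan.

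**4. Variant with censoring at the preceding scan.** Progression is detected and switchers are censored on the protocol scan grid; post-switch survival median is 6 or 12 months, cut-off 24 months, and 11 to 36% switch.
- Median time to progression 3 months: 6-month PFS 0.386–0.416 literal, 0.323–0.372 with the missed-scan rule, 0.357–0.378 with consistent censoring.
- Median 6 months: 0.595–0.618, 0.575–0.612 and 0.608–0.617. Literal and consistent rules differ by at most about 0.015 at 6 or 12 months, in either direction.

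In these scenarios 19 to 32% of post-switch deaths fall before the second missed scan. Both versions use the on-treatment grid. Off treatment, Protocol 6.3.1 schedules assessments every 12 weeks, which would push the second missed scan later and leave more deaths as events.

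**5. DOR.** The PFS rule makes a post-switch death an event; the TTP rule censors it before new therapy. SAP DOR is told to follow both while counting death as an event, and Protocol 13.4 DOR does not count death at all. The text does not determine what happens to a responder who switches and then dies.

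**The case against.** The strongest counter-argument is that the missed-assessment rule may already do the job. The summary of changes extends it to PFS, and the SAP's PFS formula takes the earliest of progression, death or censoring. A patient who switched at month 3 and died at month 15 would then be censored at about month 3, which is the result wanted. This stands as a possible reading. It defeats any flat statement that every switcher who dies becomes an event at death. It does not settle the matter: the SAP is silent on unscheduled scans, the rule's wording points to the primary endpoint, and early deaths would still be treated differently from survivors.

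A reader might infer that PFS is necessarily overstated. The documents do not support that. The sign changes between readings and with the assumed time to progression, and no switch rate, PFS median or post-switch survival is given. Protocol 9.3.14.1 also lets the investigator report rapid clinical deterioration as progression, and allows stable patients to continue past initial progression. Both may make switching without recorded progression uncommon.

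A reader might also infer that DOR simply inherits the PFS problem. It borrows from TTP as well, so its handling is indeterminate.

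Counting all deaths regardless of new therapy is a legitimate definition of PFS. The plan does not implement it coherently, because surviving switchers are censored back at their last scan and are no longer assessed for progression. Finally, silence on new therapy in Protocol 13.4 is not itself an error, since Protocol 13.0 leaves analysis definitions to the SAP.

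**Conclusion.** The point holds as a defect in the stated PFS rule. For patients who start new therapy without progression, censoring depends on later death on either reading of the SAP. TTP and best overall response in the same section do not have this problem.

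The size is modest and the direction is not fixed. In the illustration with 20% switching, 6-month PFS moves by +2.0 or −0.8 points, entirely under assumed rates. For scale, ignoring censoring, a cohort of 25 with 6-month PFS near 35% has a 95% half-width of about 1.96 × √(0.353 × 0.647 / 25) = 0.187, or 19 points. PFS and DOR are secondary and descriptive, with no formal tests. The primary ORR is untouched because best response stops at subsequent therapy.

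For DOR the conclusion is that the SAP and protocol contradict each other on whether death counts, and that the SAP adopts two incompatible censoring rules. No direction of bias can be claimed there. The rules should be corrected because the remedy is cheap and the 6-month PFS estimate is a planned output.

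**What to change.** In SAP 7.9:
- State that, for PFS and DOR, a patient who starts subsequent systemic anti-cancer therapy without prior progression is censored at the last adequate assessment on or before its start, regardless of any later progression or death. This matches what TTP already does.
- State that after a switch this rule takes precedence over the missed-assessment rule, and replace that rule's reference to the primary endpoint with the endpoints it covers.
- Give DOR one censoring rule of its own instead of a reference to both PFS and TTP.

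Align the DOR event definition between SAP 7.9 and Protocol 13.4, so that both say whether death is an event. A sensitivity analysis counting post-switch deaths, or the switch itself, as events is optional for descriptive endpoints.

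The cost is a few sentences, plus one table if the sensitivity analysis is added. The downside is a few more censored patients. Consistent censoring still assumes that switchers have the same prospects of progression as those who remain in follow-up, so the number censored for new therapy should be reported by cohort.
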